## 1.2 Connective Tissue Growth Factor

Connective tissue growth factor is a 38 kDa secreted matricellular glycoprotein of the cysteine-rich 61/CTGF/nephroblastoma overexpression (CCN) family (Perbal, 2004, Rachfal, 2005). It is produced by many cells, including fibroblasts, myofibroblasts, endothelial cells, mesangial cells, and stellate cells.

The name “connective tissue growth factor” implies a mechanism of action akin to that of classical growth factors, which signal through specific cell-surface receptors. However, experimental evidence does not support this concept. Instead, CTGF and the other members of the CCN family have activities associated with matricellular proteins that function in a more subtle modulatory fashion. Matricellular proteins, with prototypical representatives including secreted protein acidic and rich in cysteine (SPARC), osteopontin, and thrombospondins, are a subclass of ECM proteins that modulate cellular functions and signaling pathways through multiple mechanisms depending on cell type and the cellular context (Bornstein, 2002). These proteins are generally expressed at high levels during development and in response to injury; they typically bind to multiple cell-surface receptors, ECM components, growth factors, and cytokines. Connective tissue growth factor fits squarely within this definition (Chen, 2009). The cellular functions that can be modulated by CTGF include secretion and/or organization of ECM, cell proliferation, survival, adhesion, migration and EMT. Modulation of cellular signaling appears to occur through interactions of CTGF with 1) cell surface components such as integrins or the low density lipoprotein receptor-related protein (LRP)-1 (a multifunctional endocytic and signaling receptor), 2) cytokines and cytokine inhibitors, and 3) matrix components such as heparin sulfate proteoglycans (HSPGs) and fibronectin. Interactions with HSPGs may displace other HSPG-binding proteins such as VEGF and bone morphogenetic proteins (BMPs). It is believed that binding of cytokines to CTGF may either sequester them in an inactive conformation, or help to present cytokine binding partners to their receptors.

Connective tissue growth factor is a central mediator of tissue remodeling and fibrosis (Lipson, 2012). Connective tissue growth factor is essential for the fibrotic activity of TGF- $\beta$  (Mori, 1999, Wang, 2011) but it may also act independently of TGF- $\beta$ . While much has been made of the role of TGF- $\beta$  in fibrosis, studies of the role of fibronectin in pulmonary fibrosis showed that the activity of TGF- $\beta$  is dependent on cellular fibronectin to induce myofibroblast differentiation and that cellular fibronectin may have a fundamental role in activation of latent TGF- $\beta$  (Muro, 2008). Shi-wen and colleagues showed that critical activities of TGF- $\beta$  in the fibrotic process are dependent on CTGF expression, including EMT and ECM deposition,

supporting the idea that CTGF over-expression is critical for activities attributed to TGF- $\beta$  (Shi-wen, 2006).

Connective tissue growth factor has been shown to be an important mediator of pulmonary fibrosis in a mouse model of bleomycin-induced pulmonary fibrosis (Bonniaud, 2004). Lasky and coworkers observed upregulation of CTGF messenger ribonucleic acid (mRNA) gene expression in a mouse model of bleomycin-induced pulmonary fibrosis, suggesting a possible role of CTGF in the pathogenesis of lung fibrosis (Lasky, 1998).

### 1.3 Connective Tissue Growth Factor in Idiopathic Pulmonary Fibrosis

Transcripts of genes for TGF- $\beta$ 1 and CTGF were reported to be approximately 7-fold and 4-fold higher, respectively, in transbronchial lung biopsy specimens of patients with IPF compared with normal (Ziesche, 1999). TGF- $\beta$  is expressed at fibrogenic foci in IPF (Broekelmann, 1991). Increased CTGF gene expression has been described in transbronchial biopsy specimens and in bronchoalveolar lavage fluid in patients with IPF (Allen, 1999, Pan, 2001). Allen and coworkers also reported that CTGF mRNA expression is increased 10-fold in bronchoalveolar lavage fluid in patients with IPF, compared with healthy control subjects (Allen, 1999). Connective tissue growth factor in plasma was reported to be elevated in IPF patients and the abundance correlated with change in FVC (Kono, 2011). These observations suggest that CTGF may have a role in the pathogenesis of IPF.

### 1.4 Investigational Product FG-3019

FG-3019 is a fully human, recombinant DNA-derived, IgG1 kappa monoclonal antibody that binds to CTGF in the N-terminal domain 2, with high affinity ( $K_d = 0.1\text{--}0.2$  nM). The antibody, which has a molecular weight of approximately 150 kDa and contains 1326 amino acids, has been shown to interfere with the activity of CTGF. For additional information on FG-3019, please refer to the current Investigator's Brochure.

### 1.5 Clinical Trial Experience with FG-3019

The clinical trial experience with FG-3019 includes seven clinical studies that are described in the Investigator's Brochure (Version 13, 18 December 2014). Overall safety experience with FG-3019 has been favorable in studies involving subjects with IPF, pancreatic cancer, liver fibrosis due to hepatitis B, and diabetic kidney disease.

In the Investigator Brochure, exposure of subjects to FG-3019 is displayed in Table 1. Twenty one subjects with IPF received a single dose of FG-3019, 89 subjects with IPF received multiple doses in an open label trial, and 27 subjects with IPF have received multiple doses of blinded study drug (FG-3019 or placebo) in the current trial. Overall, FG-3019 has been well tolerated. Adverse events (AEs) have been generally mild or moderate in severity and transient in duration. The AEs have been typical of the subjects' underlying medical condition(s) and, in placebo-controlled studies, were equally distributed between the placebo and FG-3019 treatment groups. Infusions of FG-3019 have been well tolerated. No infusion has been stopped due to AEs. There is no apparent pattern to the SAEs observed during clinical trials, and all SAEs, except one case of pain in extremity, were considered by the Sponsor as unrelated to study drug. See the Investigator Brochure for additional information.

## 1.6 Rationale for FG-3019 in Idiopathic Pulmonary Fibrosis

The observations that CTGF is a central mediator in the process of fibrosis suggest a potential role for FG-3019 in interfering with the activity of CTGF and thereby preventing or reversing fibrotic lung damage in IPF. Connective tissue growth factor is considered a potential target for therapeutic intervention in pulmonary fibrosis ([Antoniou, 2007](#), [Ask, 2006](#), [Blom, 2002](#), [Bonniaud, 2004](#), [Grotendorst, 1997](#)).

A murine model of chronic lung fibrosis demonstrated that FG-3019 attenuated radiation-induced lung remodeling ([Huber, 2010](#)). In mice treated with FG-3019 for 8 weeks starting 3 or 16 weeks after irradiation, no tissue remodeling or fibrosis was observed 30 weeks after irradiation, and lung function, as measured by partial pressure of oxygen in arterial blood, was normalized compared with mice in the irradiated control groups. Mice treated with FG-3019 starting 16 weeks after irradiation displayed a significant reversal of lung density, which was measured by computed tomography. FG-3019 also improved survival in most groups that received FG-3019. Mice that received FG-3019 starting 3 weeks after irradiation had a survival rate of 70% at the end of the study (48 weeks after irradiation) compared with 0% survival in the irradiated controls ([Huber, 2010](#)). In another study, administration of FG-3019 to mice with bleomycin-induced pulmonary fibrosis significantly inhibited lung hydroxyproline content, a marker of lung collagen content (FibroGen, 2003, data on file).

These preclinical findings are supported by preliminary efficacy data in the FGCL-3019-049 study, which suggest that treatment of subjects with IPF with FG-3019 15 mg/kg and 30 mg/kg IV every 3 weeks is associated with improvement or stability in quantified scores of whole lung fibrosis in approximately 45 percent of subjects at 24 weeks ([Raghu, 2012](#)). Changes from baseline in these scores were significantly correlated with changes in FVC percent of predicted value ([Raghu, 2012](#)). In 2012, the FDA granted Orphan Drug Designation to FG-3019 for the treatment of IPF. A randomized, double-blind, placebo-controlled trial of FG-3019 30 mg/kg is warranted at this time to further assess safety, tolerability, and efficacy in subjects with IPF.

## **2 OBJECTIVES**

The overall objective of this study is to evaluate the safety and tolerability of FG-3019 in subjects with IPF, and the efficacy of FG-3019 for attenuating fibrosis and loss of FVC in these subjects.

### **2.1 Primary Safety Objective**

To determine the safety and tolerability of FG-3019 administered at a dose of 30 mg/kg by IV infusion every 3 weeks.

### **2.2 Primary Efficacy Objective**

To determine the effect of FG-3019 on FVC (percent of predicted value) when administered at a dose of 30 mg/kg by IV infusion every 3 weeks for 45 weeks in the target population.

### **2.3 Secondary Efficacy Objectives**

1. To evaluate the effect of FG-3019 on the extent of pulmonary fibrosis as measured by HRCT scans of the chest.
2. To evaluate the relationship between changes in quantified scores of pulmonary fibrosis and clinical outcomes.
3. To evaluate the effect of FG-3019 on progression of IPF and the frequency of respiratory-related hospitalizations and respiratory-related mortality.
4. To evaluate the effect of FG-3019 on health-related quality of life (HRQoL).

### **2.4 Exploratory Efficacy Objectives**

1. To evaluate the effect of FG-3019 on FVC (liters).
2. To evaluate the effect of FG-3019 on a panel of serum and plasma biomarkers.
3. To evaluate the relationship between known chromosomal loci associated with IPF and the response to FG-3019.

### **3 ENDPOINTS AND ASSESSMENTS**

#### **3.1 Safety Endpoints and Assessments**

- AEs and SAEs
- Laboratory test abnormalities (graded by NCI Common Terminology Criteria for Adverse Events [NCI CTCAE, v4.0])
- 12-lead electrocardiograms (ECGs)
- Physical examinations
- Human anti-human antibody (HAHA)

#### **3.2 Efficacy Endpoints and Assessments**

##### **3.2.1 Primary Efficacy Endpoint**

- Change from baseline in FVC (percent of predicted value) at Week 48.

##### **3.2.2 Secondary Efficacy Endpoints.**

- Change in pulmonary fibrosis score by quantitative HRCT at Week 24, Week 48, and later time points.
- Change from baseline in HRQoL at Week 24, Week 48, and later time points.
- Progression of IPF, defined as time from Day 1 to any one of the following:
  - Death from any cause
  - Absolute decline in FVC % of predicted value of  $\geq 10\%$  not due to intercurrent illness, confirmed by repeat spirometry.
  - Clinical diagnosis of IPF progression.
- Proportion of subjects with at least one respiratory-related hospitalization.
- Proportion of subjects with respiratory-related death, censored at Week 52.
- Categorical assessment of absolute change from baseline in FVC percent of predicted value at Week 48.

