
Statistical Methods:
	
This study is planned to enroll approximately 136 subjects, who will include a target of 110 subjects who are seeking first-line therapy and approximately 26 subjects who failed pirfenidone and/or nintedanib treatment. First line therapy is defined as no prior therapy with pirfenidone and/or nintedanib or <10% relative decrease in FVC % predicted while receiving either pirfenidone or nintedanib. Pirfenidone and/or nintedanib failure is defined as having <math>\geq 10\%</math> relative decrease in FVC % predicted during prior pirfenidone and/or nintedanib treatment. The effect of first-line treatment is the primary interest of the study and is the basis for sample size estimates. Assuming a 10% dropout rate and a common standard deviation of 7.3, a sample size of 55 subjects per arm in the primary analysis population provides approximately 80% power to detect a treatment difference of 4.2 in change from baseline to Week 48 in percent predicted FVC, using a two-sample t-test at the two-sided significance level of 0.05. If the treatment effect in the pirfenidone and/or nintedanib treatment failure group is similar to that in the general population, the two subgroups will be combined to achieve higher power.
 
The primary efficacy analysis is to compare the treatment arms in change from baseline to Week 48 in FVC % predicted. A rank ANCOVA model will be used. A repeated measures model utilizing all observed data will be used for sensitivity analyses. Logistic regression and Fisher’s exact test will be used to compare categorical endpoints. The Cox regression model will be used in time-to-event endpoints. All efficacy and safety data will be summarized descriptively by treatment arm.

	Treatment effect will be evaluated in various subgroups of interest. Unblinded analyses will be performed after all subjects have either completed the Week 48 assessments or discontinued the study.
--	---

This study will be conducted in accordance with the guidelines of Good Clinical Practice (GCP) and the applicable regulatory requirement(s), including the archiving of essential documents.

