**Figure 1. Study Schema**

#### 4.2.2 Randomized Treatment Phase

Treatment should begin within 42 days of the first screening visit. Study Drug (FG-3019 [30 mg/kg] or placebo) will be administered by IV infusion every 3 weeks for a total of 16 infusions over 48 weeks.

The schedule of assessments of safety and efficacy are provided in Appendix 1 and Appendix 2. Safety and tolerability will be monitored closely by FibroGen. Cumulative safety experience will be evaluated by FibroGen on a regular basis. Final efficacy assessment is in Week 48. Subjects who do not enter the Extended Treatment Phase will undergo end-of-study (EOS) assessment (Appendix 3) on Week 49 (4 weeks after last dose of study drug).

After all subjects complete Week 48 evaluations or prematurely discontinue the study, data will be cleaned and locked for the primary analysis of efficacy and safety.

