## 7 STUDY PROCEDURES-ALL COHORTS UNLESS OTHERWISE SPECIFIED

### 7.1 Study Procedures

The study procedures and assessments are presented for the Randomized Treatment phase in Appendix 1, for the Extended Treatment phase in [Appendix 2](#), and for End-of-Treatment and Follow-up periods in Appendix 3. See the Study Reference Manual for additional details.

The treatment period in the Randomized Treatment Phase begins on Day 1 (first infusion of Study Drug) and continues through Week 48. Visit windows are within  $\pm 3$  days of the scheduled visit date for Weeks 3 through 48.

After completion of Week 48 assessments and reporting of all AEs, subjects may be eligible to continue to open label treatment in the Extended Treatment Phase. All other subjects undergo the EOS assessments.

Eligible subjects from the Randomized Treatment Phase of the study are offered participation in the Extended Treatment Phase as described under Section [4.2.3](#) and illustrated in [Figure 1](#). A Transition Period of up to 3 weeks between the Week 48 Visit in the Randomized Treatment Phase and Day 1-EX in the Extended Treatment Phase is provided in order to determine subject eligibility for the Extended Treatment Phase and to arrange scheduling of the Day 1-EX Visit. The total interval between the Week 45 Visit in the Randomized Treatment Phase and the Day 1-EX Visit in the Extended Treatment Phase should not exceed 6 weeks. If necessary, an unscheduled visit should be performed to obtain repeat pulmonary function tests (FVC) if the interval between the Week 45 Visit in the Randomized Treatment Phase and the Day 1-EX Visit in the Extended Treatment Phase is expected to exceed 6 weeks.

The treatment period in the Extended Treatment Phase begins on Day 1-EX (first infusion of FG-3019) and continues until progression or withdrawal. Visit windows are within  $\pm 3$  days of the scheduled visit date.

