## 11.3 Procedures for Eliciting, Recording, and Reporting Adverse Events

### 11.3.1 Adverse Event Reporting Period

The study period during which all AEs and SAEs must be collected begins after informed consent is obtained and ends 4 weeks after the last dose of study drug, except for pregnancy

reporting (Section 11.3.6). In addition, all AEs reported spontaneously by the subject to site personnel, outside the study period, may be recorded.

Adverse events will be followed until resolved, stable, or until the subject's last study visit or lost to follow-up. If an AE is not resolved or stabilized at the subject's last visit, it is up to the discretion of the Investigator and study Medical Monitor to determine if further monitoring of the event is warranted.

Adverse events collected prior to dosing of study drug will be considered "non-treatment emergent" while those reported after the first dose of study drug and up to 4 weeks after the last dose of study drug will be considered "treatment emergent" and will be assessed for relationship to study drug.

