### 11.3.5.2 Deaths

For any death or life-threatening event occurring during the subject's study participation regardless of attribution, the Investigator will report the death or life-threatening event immediately to the Sponsor's Medical Monitor. The Investigator must provide an assessment of the relationship of the event to the study drug according to the guidance in Section 11.3.4.

The Investigator should notify FibroGen of any death or other SAEs occurring after a subject has discontinued or terminated study participation that may reasonably be related to this study.

If the death occurred within the SAE collection and reporting period (signed ICF to 28 days after last dose), the Investigator must submit the SAE Report Form in the same manner as described above in Section 11.3.5. Additionally, the site must complete the appropriate CRF page. This includes death attributed to progression of the subject's underlying disease.

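### Respiratory-related death is defined to Week 52, but the protocol's schedule does not follow all randomised subjects that long, and the shortfall differs by arm

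*Protocol*

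**What the plan says.** Protocol Section 3.2.2 and the Synopsis name the endpoint "Proportion of subjects with respiratory-related death, censored at Week 52". The next parts of the protocol determine who is observed, and for how long.

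- **Dosing (Section 4.2.2):** study drug is "administered by IV infusion every 3 weeks for a total of 16 infusions over 48 weeks".
- **Completers outside the extension (Section 4.2.2):** their end-of-study assessment is "on Week 49 (4 weeks after last dose of study drug".
- **Early stoppers (Section 4.2.4.1 and Appendix 3, footnote a):** the final safety assessment is 4 weeks after the last dose, within 3 days either way.
- **Event collection (Section 11.3.1):** the period "begins after informed consent is obtained and ends 4 weeks after the last dose of study drug".
- **Later deaths (Section 11.3.5.2):** the investigator should notify the sponsor of a death "occurring after a subject has discontinued or terminated study participation that may reasonably be related to this study". Neither the text nor the appendices schedule a vital-status check.
- **Extension (Sections 4.2.3.1 to 4.2.3.3):** all placebo subjects are offered it. FG-3019 subjects qualify only on FVC: a fall of under 3 points for those enrolled under the original protocol, and a value above baseline for those enrolled later. Section 7.1 allows "A Transition Period of up to 3 weeks between the Week 48 Visit" and the first extension dose.
- **Method (Synopsis):** logistic regression and Fisher's "exact test will be used to compare categorical endpoints"; Cox regression is for time-to-event endpoints.

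Section 3.2.2 also lists "Proportion of subjects with at least one respiratory-related hospitalization", with no time limit. The SAP supplied is Part 2 (extension). It refers to Part 1 for the randomised period.

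**The concern.** A proportion at a fixed week needs each subject's status at that week. Here the endpoint runs beyond the period in which the protocol collects status, for most completers outside the extension by a little and for early stoppers by a lot.

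The missing time is not random. Section 8 has the investigator remove subjects from treatment for clear progression or a confirmed FVC fall of 10 points or more, so follow-up stops early in people at raised risk of respiratory death. Eligibility for the extension, which is what carries completers past Week 49, depends on arm and on FVC. The two arms would then be compared on a mortality endpoint with unequal and outcome-related ascertainment. In Weeks 48 to 52 some placebo subjects may already be receiving FG-3019. With few events expected, one or two missed deaths can shift the comparison.

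**Working it through.** **1. The protocol's own timeline.** Sixteen infusions three weeks apart put the last at (16 − 1) × 3 = Week 45. The final visit is 45 + 4 = Week 49, which reproduces the protocol's figure.

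**2. Weeks unobserved before Week 52**, for a subject outside the extension with last dose at week w: 52 − (w + 4).

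| Last dose (week) | 0 | 12 | 24 | 36 | 45 |
|---|---|---|---|---|---|
| Weeks unobserved | 48 | 36 | 24 | 12 | 3 |

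Covering Week 52 after a Week 45 dose would need 52 − 45 = 7 weeks of follow-up, not 4. The list of key changes at the front of the protocol records that the final visit was moved from 10 weeks to 4. The former interval gave 45 + 10 = Week 55, which may be how the mismatch arose.

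**3. Crossover.** The first extension dose falls between Week 48 and Week 51 (Section 7.1: at most 6 weeks after Week 45). Placebo subjects who cross over therefore spend 52 − 51 = 1 to 52 − 48 = 4 weeks on FG-3019 before Week 52.

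**4. Scheduled observation to Week 52, by arm.** Inputs from Section 10.1: expected FG-3019 change −2.8, SD 7.3, dropout 10%. Assumptions: the change is normal, and every eligible completer accepts the extension.

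- Amendment 1 and later rule: P(change > 0) = 1 − Φ(2.8/7.3) = 0.351. Share of the FG-3019 arm: 0.9 × 0.351 = 32%.
- Original rule: P(change > −3) = 1 − Φ(−0.2/7.3) = 0.511. Share of the arm: 0.9 × 0.511 = 46%.
- Placebo, all completers eligible: up to 90%.

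The documents do not say how many subjects enrolled under each rule, so 32% to 46% is the range.

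**5. Illustrative number of deaths outside follow-up.** Section 1.1 gives 5-year survival of 20% to 40%. Assume a constant all-cause hazard h = −ln(S)/5, 136/2 = 68 subjects per arm, equal dropout (6.8 per arm, 61.2 completers) and the Amendment 1 rule. Take the mean last dose of dropouts as mid-period, Week 22.5; they are then unobserved for 52 − 26.5 = 25.5 weeks.

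| | S = 40% | S = 20% |
|---|---|---|
| h per year | 0.183 | 0.322 |
| 52-week risk, 1 − exp(−h) | 16.7% | 27.5% |
| Expected deaths per arm (68 × risk) | 11.4 | 18.7 |
| 3-week risk, 1 − exp(−3h/52) | 1.05% | 1.84% |
| 25.5-week risk, 1 − exp(−25.5h/52) | 8.6% | 14.6% |
| Dropouts, each arm (6.8 × 25.5-week risk) | 0.58 | 0.99 |
| FG-3019 completers outside the extension (61.2 × 0.649 = 39.7, × 3-week risk) | 0.42 | 0.73 |
| Outside follow-up, FG-3019 | 1.0 | 1.7 |
| Outside follow-up, placebo (all roll over) | 0.6 | 1.0 |

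Both arms together: 1.6/22.8 = 7.0% and 2.7/37.4 = 7.3%. These are all-cause deaths; respiratory deaths would be fewer.

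**The case against.** The best reply has four parts.

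- **SAP Part 1 may settle the analysis.** It was not available, and the word censored in the endpoint leaves room for a time-to-event method. The Synopsis does not assign this endpoint to Fisher's test or logistic regression by name. A reader might infer that unobserved subjects will simply be counted as survivors; the documents do not say so. This stands as regards method. It does not answer the gap, because no analysis rule can supply vital status that was never collected. Censoring at last contact would be possible, but it would be informative and would no longer give the stated proportion.
- **Many subjects are seen past Week 49.** A reader might infer that follow-up stops at Week 49 for everyone, or that crossover hides placebo deaths. Neither is right: extension entrants remain under observation, and crossover affects which treatment a late death occurs on, not whether it is seen.
- **Later deaths may still come to light.** Section 11.3.1 lets sites record events reported spontaneously after the study period. That is optional and gives no systematic ascertainment.
- **The importance is limited.** This is one of several secondary endpoints in a Phase 2 trial, and confirmed FVC decline and clinical progression already count as events in the progression endpoint. That is fair, but it does not make respiratory death observable to Week 52.

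**Conclusion.** The mismatch holds on the protocol's own timeline: respiratory-related death to Week 52 cannot be observed for all randomised subjects. The gap is 3 weeks for completers outside the extension and can be 24 weeks or more for early stoppers. It is informative, and it differs by arm.

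The estimated size is modest: about 7% of all-cause deaths, or 1.0 to 1.7 on FG-3019 and 0.6 to 1.0 on placebo, of about 11 to 19 expected per arm. It rests on a constant hazard taken from general IPF survival, equal dropout, mid-period stopping and the Amendment 1 rule, so it is an illustration only.

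A reader might infer that missed deaths fall mainly on placebo and pull the comparison toward no difference. The documents do not support that. It presumes that FG-3019 works and that progression removals are therefore commoner on placebo. The extension rule acts the other way: with equal dropout, the extra 0.4 to 0.7 missed deaths are all on FG-3019. The direction is not predictable. A larger loss, such as one death in ten, would follow only if the Week 49 to 52 gap were applied to everyone, including extension entrants, or if dropout above the protocol's 10% were assumed.

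**What to change.** Move the cut-off for the randomised comparison of respiratory death from Week 52 to Week 48, before any extension dose. Obtain vital status and cause of death at Week 48, by telephone or from records, for every randomised subject, including early stoppers. The proportion can then be analysed as stated, and a switch to Kaplan-Meier or Cox is not needed.

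Apply the same Week 48 cut-off to respiratory hospitalisation, and ask about it at the same contact.

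If status stays unknown for some subjects, do not count them as non-events. Report their number by arm and add a time-to-event sensitivity analysis censored at last contact, noting that this censoring may be informative and that non-respiratory death is a competing event.

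The cost is a change of wording in the protocol and SAP, one contact or records check per early stopper, and the loss of the last 4 weeks of events. The primary endpoint and sample size do not change.
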